## 4.2 Exclusion Criteria

1. Any significant medical condition, including any suggested by screening laboratory findings that, in the opinion of the Investigator or Sponsor, may place the subject at undue risk from the study, including but not necessarily limited to uncontrolled hypertension and/or diabetes, clinically significant pulmonary disease (e.g., chronic obstructive pulmonary disease

- requiring hospitalization within 3 months) or neurological disorder (e.g., seizure disorder active within 3 months).
2. Documented history of a cerebral vascular event (stroke or transient ischemic attack), unstable angina, myocardial infarction, or cardiac symptoms consistent with New York Heart Association (NYHA) Class III–IV (refer to [Appendix 13.5](#)) within 6 months prior to their first dose of study drug.
  3. Recent or ongoing serious infection, including:
    - a. Any active Grade 3 or higher (according to NCI CTCAE version 4.03) viral, bacterial, or fungal infection within 2 weeks of the first dose of the study drug. Routine antimicrobial prophylaxis is permitted.
    - b. Known seropositivity for or active infection by human immunodeficiency virus (HIV).
    - c. Active Hepatitis B (by surface antigen expression or polymerase chain reaction) or Hepatitis C (by polymerase chain reaction) infection or on hepatitis-related antiviral therapy within 6 months of first dose of study drug.
  4. Female subject who is pregnant, breastfeeding, or is considering becoming pregnant during the study or for approximately 6 months after the last dose of study drugs.
  5. Male subject who is considering fathering a child or donating sperm during the study for approximately 6 months after the last dose of study drugs.
  6. Systemic therapy with corticosteroids at >20 mg/day prednisone or equivalent within 1 week prior to the first dose of study drug.
  7. History of another invasive malignancy that has not been in remission for at least 3 years. Exceptions to the 3-year limit include non-melanoma skin cancer, curatively treated localized prostate cancer, ductal carcinoma *in situ*, and cervical cancer *in situ* on biopsy or squamous intraepithelial lesion on PAP smear.
  8. Prior exposure to a pyrrolobenzodiazepine (PBD)-based drug, prior participation in a rovalpituzumab tesirine clinical trial, or known hypersensitivity to rovalpituzumab tesirine or excipient contained in the drug formulation, unless undergoing retreatment with rovalpituzumab tesirine in the context of this protocol.

### 4.3 Contraception Recommendations

In WOCBP, pregnancy testing will be conducted at scheduled time points during screening and the course of the study (refer to [Appendix 13.1](#)). Pregnancy testing guidelines are outlined in [Section 7.2.9](#).

#### 4.3.1 Contraception for Female Subjects

If female, subject must be either postmenopausal or permanently surgically sterile (refer to [Inclusion Criteria 12](#)) OR a WOCBP, practicing at least one of the following methods of birth control, on Study Day 1 (or earlier) through at least 6 months after the last dose of study drug.

- Combined (estrogen and progestogen containing) hormonal contraception (oral, intravaginal, transdermal) associated with the inhibition of ovulation, initiated at least 1 month prior to Study Day 1.
- Progestogen-only hormonal contraception (oral, injectable, implantable) associated with inhibition of ovulation, initiated at least 1 month prior to Study Day 1.
- Bilateral tubal occlusion/ligation.
- 
- Vasectomized partner(s), provided the vasectomized partner verbally confirms receipt of medical assessment of the surgical success, and is the sole sexual partner of the WOCBP trial participant.
- Intrauterine device (IUD).
- Intrauterine hormone-releasing system (IUS).
- True abstinence: Refraining from heterosexual intercourse when this is in line with the preferred and usual lifestyle of the subject [periodic abstinence (e.g., calendar, ovulation, symptothermal, post-ovulation methods) and withdrawal are not acceptable].

#### **4.3.2 Contraception for Male Subjects**

Male subjects who are sexually active with a WOCBP, even if the male subject has undergone a successful vasectomy, must agree from Study Day 1 through at least 6 months after the last dose of study drug to use condoms and his female partner(s) must use at least one of the contraceptive measures (as defined in the protocol for female study subjects of childbearing potential).

Male subject agrees not to donate sperm from Study Day 1 through at least 6 months after the last dose of study drug.

#### **4.4 Removal of Subjects from Therapy or Assessment**

The Sponsor or its designee must be notified if a subject is withdrawn from study treatment or from the study. The reason(s) for withdrawal must be documented in the subject's medical records and case report form (CRF). When a subject withdraws from treatment, all safety data normally required at the end of the study (i.e., the end-of-treatment visit and long-term follow-up) will be obtained if possible.

#### **4.4.1 Discontinuation of Study Drug**

Treatment with study drug may be discontinued for any of the following reasons:

- Progressive disease (PD) per RECIST 1.1
- Adverse event
- Physician decision
- Study terminated by sponsor
- Withdrawal by subject
- Other

#### **4.4.2 Subject Discontinuation from Study**

Any subject may be discontinued from the study for any of the following reasons:

- Withdrawal by subject
- Death
- Physician decision
- Lost to follow-up
- Study terminated by Sponsor
- Other

## **5. Treatments**

### **5.1 Treatments Administered**

Rovalpituzumab tesirine, the investigational agent under study in this protocol, is an ADC. Detailed information describing the preparation, administration, and storage of rovalpituzumab tesirine is located in the Pharmacy Binder.

### **5.2 Investigational Product: Rovalpituzumab Tesirine**

#### **5.2.1 Description**

Rovalpituzumab tesirine drug product is provided in a sterile clear USP Type I 10 mL glass vial and includes histidine hydrochloride, sucrose and polysorbate 20. A complete description of the chemistry and formulation are provided in the Investigator's Brochure.

#### **5.2.2 Packaging and Labeling**

Rovalpituzumab tesirine is provided in sterile clear USP Type I, 10 mL glass vials. The vials and/or primary vial carton will have labels bearing the appropriate label text as required by governing regulatory agencies.

#### **5.2.3 Dosing**

The actual dose is based on the subject's actual body weight on C1D1 to the nearest kilogram, and administered according to the assigned dose. If the subject's actual weight at subsequent cycles is within 10% of the C1D1 weight, the dose will not be adjusted due to weight changes. Otherwise, the dose will be adjusted based on the actual body weight to the nearest kilogram at that cycle. Rovalpituzumab tesirine will be administered intravenously (IV) over 30 minutes (treatment window: 20 to 40 minutes) on Day 1 of each 6-week cycle.

Subjects must meet all of the following on each dosing day before receiving study drug:

- ANC  $\geq$ 1,000/ $\mu$ L
- Platelet count  $\geq$ 75,000/ $\mu$ L
- Resolution to Grade 0 or 1, or to baseline grade if pre-existing, of any clinically-significant AEs or laboratory abnormalities occurring during the previous cycle

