## 1.4 Rationale for the Study and Anticipated Risks

Rovalpituzumab tesirine may be effective in multiple cancers that express DLL3. This study will explore further the safety, tolerability, and potential therapeutic utility of rovalpituzumab tesirine in subjects with such non-SCLC DLL3+ tumors, with the intent to provide the basis for further development of rovalpituzumab tesirine in one or more of these evaluated indications.

As of 30 June 2016, 104 subjects (SCLC or LCNEC) had received at least one dose of rovalpituzumab tesirine at doses ranging from 0.05 mg/kg to 0.8 mg/kg on an every 3 weeks (Q3wk) schedule (34 subjects) and 0.3 mg/kg to 0.4 mg/kg on an every 6 weeks (Q6wk) schedule (70 subjects).

The most frequently reported treatment-emergent adverse event (TEAE) terms in all treated subjects were fatigue (49%), pleural effusion (34%), and dyspnea (31%); the most frequently reported TEAE terms considered related to rovalpituzumab tesirine by the Investigator were fatigue (35%), pleural effusion (28%), and peripheral edema (26%).

The most frequently reported Grade 3/4 TEAEs were dyspnea (14%), pleural effusion (12%), and fatigue (11%); the most frequently reported Grade 3/4 TEAEs considered related to rovalpituzumab tesirine were pleural effusion and thrombocytopenia (10% each), and fatigue and increased lipase (6% each).

Serious adverse events (SAEs) were reported in 49 subjects (47%), 26 (25%) were considered related to rovalpituzumab tesirine by the Investigator. The most common SAE was pleural effusion, occurring in 18 subjects (17%); all occurrences were considered related to rovalpituzumab tesirine. The second most common related SAE was pericardial effusion, in 8 subjects (8%). Six subjects experienced a fatal AE, 2 of which were considered related to rovalpituzumab tesirine (acute kidney injury and tumor hemorrhage).

Preclinical toxicology studies conducted in the rat and the cynomolgus monkey have identified the bone marrow, lung, and kidney as a potential source of clinical adverse events (AEs) (refer to Section 4.3.1 of the current Rovalpituzumab Tesirine Investigator's Brochure [IB]; Stemcentrx data on file). Accordingly, safety assessments will include regular assessments at protocol-specified time points of routine physical examination, laboratory and imaging tests, as well as echocardiograms (ECHOs), a fluid retention questionnaire, daily weights, and untimed (spot) analysis of protein.

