#### **5.2.4 Dose Modifications**

Information and guidelines regarding Part A dose-regimen finding, including information regarding DLTs and the methods for determination of the MTD, are provided in [Section 3.1.1](#). Information regarding Part B expansion cohorts is provided in [Section 3.1.2](#).

Instructions for dose modifications for individual subjects in the Part A dose-regimen finding and Part B expansion groups are the same. No intrasubject dose escalation will be permitted. Adjustments to Dose Modification Guidelines may occur based on the clinical judgment of the Investigator with approval from the Medical Monitor.

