#### **5.2.4.3 Dose Reductions Due to Adverse Events**

Subjects who experience a Grade 3 or 4 AE (unless the AE is determined to be clearly unrelated to study drug) should have a dose reduction in subsequent treatment cycles to dose level -1 or -2, or as suggested following discussion with the Medical Monitor and/or Sponsor. If the Grade 3 or 4 AE recurs after dose reduction, study treatment must be permanently discontinued. [Table 5-1](#) displays specific toxicities requiring dose reduction and/or discontinuation. Adjustments to these guidelines may occur based on the clinical judgment of the Investigator and with approval of the Medical Monitor.

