**Table 5-1 Toxicities Requiring Dose Reduction**

Toxicities Requiring 1 Dose Level Reduction at First Occurrence	

 
– 2nd occurrence = 2nd dose level reduction
 
– Discontinue after 2 dose level reductions
 
	
Serosal Effusions and Edema	
 
• Grade 2 or higher pericardial effusion
 
• Grade 2 or higher pleural effusion
 
• Grade 2 or higher ascites
 
• Grade 2 or higher peripheral edema
 

Hematology	
 
• Grade 3 thrombocytopenia (platelets <math><50.0\text{--}25.0 \times 10^9/\text{L}</math>)
 
• Grade 4 neutropenia (ANC <math><0.5 \times 10^9/\text{L}</math>) lasting more than 7 days
 
• Grade 3 or higher febrile neutropenia (with ANC <math><1.0 \times 10^9/\text{L}</math>) (concurrent fever <math>\geq 38.3^\circ\text{C}</math>)
 

Laboratory Abnormalities	
 
• Clinically significant Grade 3 or higher non-hematologic laboratory abnormality that does not resolve to Grade 0/1 or baseline within 7 days
 
• Any other Grade 3 or 4 laboratory abnormality considered clinically significant and treatment-related; adjustments to these guidelines may occur based on the clinical judgment of the Investigator and with approval of the Medical Monitor and Sponsor
 
• Grade 2 hypoalbuminemia
 

Other Adverse Events	
 
• Grade 3 photosensitivity reaction (Section 5.5.2)
 
• Grade 3 or Grade 4 nonlaboratory treatment-related toxicity, with the exception of fatigue, asthenia, nausea, or other manageable constitutional symptom
 

Toxicities Requiring 2 Dose Level Reductions at First Occurrence	

 
– Discontinue at second occurrence
 
	

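### Section 5.2.3 recalculates the mg dose on actual weight with no exception for fluid, so from Cycle 2 on retained fluid can raise the dose or make a reduction smaller in mg

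*Combined protocol and SAP*

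**What the plan says.** Section 5.2.3 sets the Cycle 1 dose from the weight on C1D1. For small later changes the rule is "within 10% of the C1D1 weight, the dose will not be adjusted due to weight changes". For larger ones it is "Otherwise, the dose will be adjusted based on the actual body weight to the nearest kilogram at that cycle". The second rule is mandatory and does not ask why the weight changed.

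The same section sets conditions for each dosing day. One is "Resolution to Grade 0 or 1, or to baseline grade if pre-existing, of any clinically-significant AEs or laboratory abnormalities occurring during the previous cycle". Section 5.2.4.1 also allows treatment to proceed above Grade 1 when the event is clearly unrelated to study drug or the toxicity is adequately managed. It asks that drained effusions be stable or improved for at least 2 weeks. None of these conditions refers to weight.

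Table 5-1 requires a one-level reduction for "Grade 2 or higher peripheral edema" and for effusions and ascites of the same grades, and a two-level reduction for Grade 3 effusions and edema. Section 5.2.4.3 says that subjects with a Grade 3 or 4 AE not clearly unrelated to study drug "should have a dose reduction in subsequent treatment cycles to dose level -1 or -2". The levels in Table 3-1 are 0.2, 0.3 and 0.4 mg/kg. No reduction rule names the weight to multiply by, so Section 5.2.3 governs.

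Two general statements stand in Section 5.2.4: "No intrasubject dose escalation will be permitted", and "Adjustments to Dose Modification Guidelines may occur based on the clinical judgment of the Investigator with approval from the Medical Monitor". Neither mentions weight.

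**The concern.** The protocol treats weight gain in two ways. Section 5.5.4 asks sites to watch it as a possible sign of fluid retention, and daily weights and a fluid retention questionnaire are collected for that purpose. Section 5.2.3 treats the same gain, once above 10%, as a reason to give more drug.

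Fluid retention is an established effect here. Section 1.4 reports related pleural effusion in 28% and related peripheral edema in 26% of 104 treated subjects. So a toxicity of the drug can raise the next dose, or weaken in mg the reduction meant to answer it. What is at stake is safety over several cycles. Section 3.2.3 says the SCLC recommended dose was chosen on the toxicity and efficacy profile during multiple-cycle dosing, and later cycles are where this rule acts.

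**Working it through.** **Inputs.** Dose levels of 0.2, 0.3 and 0.4 mg/kg come from Table 3-1. The 10% band and rounding to the nearest kilogram come from Section 5.2.3. The documents give no body weights or weight gains, so those below are assumptions. The plan states no figure on this point to reproduce.

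**Formulas.** Dose in mg = level × dosing weight. Dosing weight = C1D1 weight if the change is within 10%, otherwise actual weight to the nearest kilogram. Where the previous dose was on C1D1 weight, the net cut = 1 − (new level × new weight) / (old level × C1D1 weight).

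**Trigger.** For 70 kg, 110% is 77.0 kg, so the first whole kilogram above it is 78 kg (+11.4%). For C1D1 weights of 50, 60, 80 and 90 kg it is 56, 67, 89 and 100 kg (+12.0%, +11.7%, +11.3%, +11.1%).

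**Same level.** 0.3 × 70 = 21.0 mg; 0.3 × 78 = 23.4 mg; 23.4 / 21.0 = 1.114, or +11.4%.

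**Reduction given at 78 kg, previous dose on 70 kg.**

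| Step (mg/kg) | Cut on C1D1 weight | Cut at 78 kg | mg lost from the cut |
|---|---|---|---|
| 0.3 to 0.2 | 1 − 14.0/21.0 = 33.3% | 1 − 15.6/21.0 = 25.7% | 1.6 of 7.0 |
| 0.4 to 0.3 | 1 − 21.0/28.0 = 25.0% | 1 − 23.4/28.0 = 16.4% | 2.4 of 7.0 |
| 0.4 to 0.2 | 1 − 14.0/28.0 = 50.0% | 1 − 15.6/28.0 = 44.3% | 1.6 of 14.0 |

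**Previous dose already raised for fluid.** From 0.3 × 78 = 23.4 mg, a cut to 0.2 mg/kg at 78 kg gives 15.6 mg. That step is 7.8 mg, or 33.3%, and is not smaller. The new dose still exceeds the 14.0 mg that C1D1 weight would give.

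**Sensitivity.**
- C1D1 weights of 50 to 90 kg at the whole-kilogram trigger: cuts of 25.3–25.9%, 16.0–16.7% and 44.0–44.4% for the three steps.
- If the 10% test uses unrounded weight, 77.1 kg triggers and is dosed as 77 kg: same-level dose +10.0%; cuts of 26.7%, 17.5% and 45.0%.
- A 20% gain: same-level dose +20%; cuts of 20.0%, 10.0% and 40.0%.
- A one-level cut is fully cancelled only at a gain of 33% (0.4 to 0.3) or 50% (0.3 to 0.2).

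**Comparison with the existing band.** The raised dose of 23.4 mg is 23.4/70 = 0.334 mg/kg of C1D1 weight. A subject who falls from 70 to 63 kg stays on 21.0 mg, which is 21.0/63 = 0.333 mg/kg of current weight. Near the trigger, the two are almost the same size.

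**The case against.** The strongest case against is that the opening is narrow and already guarded. The fluid-raised dose needs a gain of more than 7 kg at 70 kg, mostly fluid, in a subject who may still be dosed. Most Grade 2 or higher fluid events are held or reduced. Table 5-1 also reduces for Grade 2 hypoalbuminemia, and by two levels for capillary syndrome and severe hypoalbuminemia. Diuretics and corticosteroids are provided for, and the SMC reviews cumulative safety. The 28% and 26% are all-grade figures from SCLC and LCNEC subjects on several doses and schedules, so they do not say how often this arises. Appendix 13.8 reproduces only some CTCAE terms, so the documents do not show whether so large a gain would itself be graded above 1. All of this stands as a limit on frequency. It does not close the opening: the edema and effusion grades that are reproduced are not defined by body weight, and no dosing condition requires weight to return to baseline.

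A second objection is that levels are in mg/kg, so the subject gets exactly the level prescribed, and no percentage cut in mg is promised. That is correct. The comparison with C1D1 weight is a yardstick chosen for this review, and it matters only because the extra kilograms may be the toxicity itself.

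A third is that Section 5.2.4 already covers the case. Investigator discretion with Medical Monitor approval can reach a reduction, but it works case by case and does not clearly reach the Section 5.2.3 calculation. A reader might infer that the bar on intrasubject escalation either forbids the higher mg dose or is contradicted by it. The text supports neither firmly, because it does not mention weight and the levels are in mg/kg.

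**Conclusion.** The point holds as a minor safety improvement. As written, Section 5.2.3 makes retained fluid count as dosing weight once the gain passes 10%. In the 70 to 78 kg example the same-level dose rises by 11.4%. If the previous dose was on pre-fluid weight, the three reductions are 25.7%, 16.4% and 44.3% in mg instead of 33.3%, 25.0% and 50.0%. This rests on illustrative weights, on the subject passing the dosing conditions, and on the gain being mainly fluid.

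Stronger readings are not supported:
- A reader might infer that required reductions are undone. They are not at these gains.
- A reader might infer that the excess grows without limit. The rule has no cap, but larger retention tends to reach grades that are held or reduced.
- A reader might connect the rule with the fatal generalized edema in Section 5.5.4. The documents make no such link.
- A reader might doubt the MTD. Recalculation applies only at later cycles, so Cycle 1 DLT counts are unaffected.

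**What to change.** Add to Section 5.2.3:

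> If the Investigator attributes a weight gain above 10% from C1D1 mainly to edema, effusion or ascites, the dose is not increased for weight. It is calculated on the most recent dosing weight recorded before the fluid retention (the C1D1 weight if the dose has not since been adjusted for weight), and any Table 5-1 reduction is calculated on that same weight.

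In the example, the dose stays at 21.0 mg, and a cut to 0.2 mg/kg gives 14.0 mg, the full 33.3%. The wording names one weight, so sites need not choose.

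The cost is one sentence and no new data: the daily weight diary (Section 7.2.8) and the fluid retention questionnaire (Section 7.2.7, Appendix 13.9) already exist. The downside is that the Investigator must judge the cause, with no numeric test for what counts as mainly fluid. A true gain in body mass misattributed to fluid would be dosed slightly low, at 21.0 instead of 23.4 mg. The sentence does not address fluid already present at C1D1.

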#### **5.2.4 Dose Modifications**

Information and guidelines regarding Part A dose-regimen finding, including information regarding DLTs and the methods for determination of the MTD, are provided in [Section 3.1.1](#). Information regarding Part B expansion cohorts is provided in [Section 3.1.2](#).

Instructions for dose modifications for individual subjects in the Part A dose-regimen finding and Part B expansion groups are the same. No intrasubject dose escalation will be permitted. Adjustments to Dose Modification Guidelines may occur based on the clinical judgment of the Investigator with approval from the Medical Monitor.

#### **5.2.4.1 Dose Holds or Delays**

Subjects who experience DLT in Cycle 1 should not receive further treatment with study drug unless clinical benefit is demonstrated with adequately managed toxicity and there is approval from the Medical Monitor and/or Sponsor. The subsequent dose level will be defined by the Medical Monitor and/or Sponsor in discussion with the site Investigator in the context of the type of AE observed.

If a subject has a clinically significant, unresolved AE on Day 1 of Cycle 2 or beyond, the start of the cycle may be delayed for up to 12 weeks. Longer dose delays may be permitted with the approval of the Medical Monitor if there was no documented PD. The AE must resolve to baseline or  $\leq$ Grade 1 prior to proceeding with treatment, unless the AE is determined to be clearly unrelated to study drug, or toxicity has been adequately managed.

Serosal effusions (e.g., pleural, pericardial, or ascites) that have been drained should remain stable or improved for at least 2 weeks prior to resumption of dosing (refer to [Table 5-1](#), below).

#### **5.2.4.2 Clinical Monitoring of Grade 3 or Grade 4 Adverse Events**

Subjects who experience Grade 3 or 4 non-laboratory AEs will require weekly or more frequent clinical assessments, as appropriate. The assessments should include review of AEs, concomitant medications, vital signs, weight, physical examination, ECOG performance status, laboratory and other testing, as clinically appropriate.

Subjects who experience Grade 3 or 4 hematologic AEs should have repeat complete blood count (CBC) assessment at least every 3 days or more frequently, as clinically appropriate, until resolution of hematologic toxicity to Grade 2 or lower.

Subjects who experience Grade 3 or 4 non-hematologic laboratory AEs will require more frequent laboratory assessments, as clinically appropriate, until resolution of the AEs.

Subjects who experience Grade 3 or 4 laboratory abnormalities may require more frequent laboratory assessments, as clinically appropriate.

